11.11.2 Potential risks of study drug and the research and management guidelines

In case of grade 3/4 intolerance related to raltegravir and/or etravirine, one or both drugs should be interrupted and the baseline ARV regimen might be reintroduced once the event is resolved or once the related clinical and/or biological symptoms are enough improved.

No raltegravir and/or etravirine dosage adaptation will be authorized. Upon investigator's opinion, an additional clinical visit might be scheduled within 2 to 4 weeks following the onset of the event to control the symptoms evolution.

In case of raltegravir and/or etravirine treatment related grade 1/2 adverse event, a symptomatic treatment can be proposed.

Particular attention to the following symptoms (see below), related to raltegravir and/or etravirine, will be requested. In case of grade 3/4 (please refer to Appendix A6 for a definition) suspected treatment will be discontinued:

- Skin reaction and severe hypersensitivity (such as: Stevens-Johnson syndrome, erythema multiforme (EM))
- Psychiatric effects (such as: depression, suicide attempt, suicidal behavior and suicidal thoughts)
- Metabolism disorder (such as: diabetes, hyperglycemia, hyperlipidemia)
- Heart conditions (such as: myocardial infarction)

11.11.3 Management of lipid metabolism impairment

In case of mild increase of the lipid parameters, a dietary regime will be proposed. Concomitant lipid-lowering treatments with fibrates or statins are needed. They will have to be prescribed according the guidelines, taking into account the potential interactions with cytochrome P450 based enzymes.

11.11.4 Management of glycaemia impairment

In case of onset of hyperglycaemia or diabetes, an appropriate treatment should be proposed with a dietary regime, physical exercise and anti-diabetic drugs if needed.

11.11.5 Management of pregnancy

In case of suspicion of pregnancy during the trial, a pregnancy test should be performed immediately. Pregnancy must be notified to the sponsor and the methodology centre (see section 13.2.4).

If a female participant becomes pregnant, all study drugs that are not recommended during pregnancy based on the latest SmPC (Summary of the Product Characteristics) must be discontinued. Women should receive regimens that are authorised during pregnancy.

12 BIOLOGICAL SAMPLES AND STORAGE

12.1 Schedule of sample's collection

	W-6/W-4	D0	W2	W4	W12	W24	W36	W48	W64	W80	W96	EOT	In case of virological failure	Volume collected	Aliquots to be prepared	Location of sample's analysis
HBV/HCV serology	√													2 tubes of 3mL	According to the local virology laboratory procedures	Local virology laboratory
Genotypic resistance on blood DNA	√													1 tube of 7mL		
HIV-RNA plasma Viral Load	√	√		√	√	√	√	√	√	√	√	√		1 tube of 7mL		
Urinary pregnancy test If positive: β HCG	√	√	√	√	√	√	√	√	√	√	√	√		/		
Urine analysis	√			√	√	√		√		√	√	√		/		
Whole blood cells count	√					√		√		√	√	√		1 tube of 3mL		
CD4/CD8 Lymphocytes	√	√			√	√		√		√	√	√		1 tube of 3mL		
Creatinine, AST, ALT, CPK, Bilirubin	√			√	√	√		√		√	√	√		1 tube of 3mL		
Lipid profilefasting glyceemia		√		√	√	√		√			√	√		3 tubes of 3mL	3-4 aliquots of 1.2mL of EDTA plasma	Pr [name]/ [name] [name], Service de Virologie - Groupe Hospitalier Pitié-Salpêtrière
Concentrations of ARVs in Plasma/ Genotypic resistance on blood RNA													√	2 EDTA tubes of 7mL		
Seminal sub-study								√						/		

Sample bank centralized and stored at Biobank

Plasma bank		√	√	√	√	√	√	√	√	√	√	√		3 EDTA tubes of 7mL	6-7 aliquots of 1.2mL of EDTA plasma	1 aliquot of 1.2 mL to measure ARVs concentration in Plasma → [name] [name], Laboratoire de Pharmacologie Clinique - Hôpital Bichat-C. Bernard
Concentrations of ARVs in Plasma/ Genotypic resistance on blood RNA													√	1 EDTA tube of 7mL	3-4 aliquots of 1mL EDTA plasma	[name] [name] and Pr [name]/ [name] [name], Laboratoire de Pharmacologie Clinique - Hôpital Bichat-C. Bernard Service de Virologie -Groupe Hospitalier Pitié-Salpêtrière
Immunologic analysis of inflammation markers		√						√			√	√		1 EDTA tube of 7mL	3-4 aliquots of 1mL EDTA plasma	Pr [name], CDR Saint-Antoine Faculté de Médecine et Université Pierre et Marie Curiesite Saint-Antoine
														1 citrate tube of 5mL	2 aliquots of 1mL citrate plasma	
														1 dry tube of 5mL	2-3 aliquots of 1mL of serum	
Total cell-associated HIV-DNA quantification		√						√			√	√		1 EDTA tube of 7mL	3 aliquots of 2mL of whole blood sample	Pr [name]/ [name] [name], Service de Virologie - Groupe Hospitalier Pitié-Salpêtrière
Total blood volume	29	67	21	40	43	46	28	70	28	37	70	53	21			

collected (mL)												
----------------	--	--	--	--	--	--	--	--	--	--	--	--

12.2 Blood samples preparation for HIV-DNA quantification and plasma storage

The blood samples collected during the patients' visits as defined above will be transferred to the virology laboratories of the participating sites using EDTA (Ethylene Di-Amine Tetra-Acetate) tubes (3,4,5 tubes of 7 mL according to the visit) with an additional citrate and dry tube (1 tube of 5 mL each) according to the visit.

A trial-specific form inside the eCRF will ensure the traceability of the collected samples from the clinical site to the virology laboratory mentioning:

- Patient's name
- Patient's identification code
- Site's number
- Date and number of the patient's visit

Plasma and serum bank preparation and storage:

- At each time point, 6-7 plasma aliquots of 1,2 mL (EDTA tube) will be precisely measured. Additional 3-4 plasma aliquots of 1 mL (EDTA tube), 2 aliquots of 1mL (citrate tube), 2-3 aliquots of 1mL of serum (dry tube), depending the visit, will be prepared.
- The plasma aliquots will be stored in 2 mL NUNC- vials
- The vials will be identified using anonymized labels mentioning only patients' identification codes, sites numbers, number and dates of each visits
- Prepared samples will be cryopreserved at -80°C

Preparation of whole blood samples for total cell-associated HIV-DNA quantification:

- Whole blood samples will be slowly and gently blended for homogeneity
- 3 whole blood aliquots of 2mL will be precisely measured
- The plasma aliquots will be stored in 2 mL NUNC vials
- The vials will be identified using anonymized labels mentioning only patients' identification codes, sites numbers, number and dates of each visits
- Prepared samples will be cryopreserved at -80°C

12.3 Evaluated parameters

12.3.1 Evaluation of the glucid and lipid metabolism

The evolution of the glucid and lipid metabolism will be evaluated by measuring the fasting glycemia, triglycerides, total-cholesterol, LDL-cholesterol and HDL-cholesterol. At visit at which these parameters will be measured, the median values and the proportion of patients above the upper normal will be reported and analyzed.

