5.4 Raltegravir and etravirine: benefits and advantages in terms of toxicity

5.4.1 Raltegravir (RAL)

Raltegravir (RAL, Isentress® MK-0518), was the first approved integrase inhibitor in 2008 in treatment naïve and experienced HIV infected individuals.

– In the STARTMRK study, the proportion of treatment-naïve patients who achieved virological suppression in the raltegravir arm was 86.1% at 48 weeks, non-inferior to a TDF (Tenofovir) /FTC (Emtricitabine)/EFV (Efavirenz). Importantly this efficacy rate was maintained over 5 years with a trend towards superiority over efavirenz mainly due to a better tolerability on long term [50]. More recently, raltegravir was compared to dolutegravir, a new integrase inhibitor currently in development, in treatment naïve patients in the SPRING 2 study which displays one of the highest efficacy rate with 85% and 88% of viral suppression (< 50 copies/mL at W48), respectively [51].

- Raltegravir is characterized by an excellent tolerability profile.

In all randomized clinical trials, the safety and the tolerability of raltegravir were excellent and the rate of side effects has been low [52]. The most common adverse events reported were: headache, other nervous system effects and gastrointestinal events and the majority were mild and transient in nature.

The most important superiority in terms of long-term tolerability is the metabolic profile of raltegravir. Raltegravir is a drug with an excellent metabolic profile [53-54]. In patients initiating ART with raltegravir in the STARTMRK trial, there were no significant changes from baseline in fasting total cholesterol, LDL-cholesterol, HDL-cholesterol, and triglyceride levels. There was a trend toward a greater decrease from baseline in the total cholesterol:HDL-cholesterol ratio for raltegravir (−0.20) than efavirenz (+0.04) recipients (p=0.06) in a previously treatment-naïve population [55].

- Switch studies

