9.2 Secondary Endpoints

Biological efficacy

- Percentage of patients remaining in therapeutic success up to week 48 and week 96 defined as the absence of virological failure and the absence of treatment interruption due to adverse event judged by DSMB as related to the trial treatment or procedure
- Percentage of patients in virological success (plasma HIV-RNA \leq 50 copies/mL) up to week 96
- Percentage of patients with trial treatment interruption
- Percentage of patients with plasma HIV-RNA VL between 51 and 200 copies/mL and percentage of patients with plasma HIVRNA VL > 200 copies/mL at time of virological failure
- Median time of virological failure (time limit between the date of the study treatment initiation and the date of virological failure)
- Percentage of patients with RAL and/or ETR resistance mutations in case of virological failure and percentage of patients with resistant viruses to all study drug's class in case of virological failure
- Factors associated with the occurrence of plasma HIV-RNA VL > 50 copies/mL (genotype history, pre-cART VL, plasma drug concentration (etravirine, raltegravir) at the virological rebound, viral reservoir measured by HIV-DNA at D0 and adherence assessed with a self-questionnaire)
- Evolution of total cell-associated HIV-DNA from D0 to W48 and W96
- Evolution of CD4+, CD8+ T cells counts and CD4/CD8 ratio at each time point from D0

Tolerability and Metabolic Impact

- Percentage of patients with at least one serious adverse event as judged by DSMB as related to the trial treatment or to the trial strategy
- Percentage of patients with grade 3 or grade 4 clinical and biological adverse events
- Evolution of metabolic parameters (fasting triglycerides, total cholesterol, HDL-cholesterol, LDL-cholesterol and fasting glycemia)
- Evolution of the calibrated Framingham risk score and of the SCORE risk equation including HDL cholesterol (from the European Cardiovascular Society) from D0 to W48 and W96
- Evolution of renal function measured using proteinuria and the CKD-EPI (Chronic Kidney Disease Epidemiology Collaboration Calculator) formula to estimate the Glomerular Filtration Rate (GFR) from D0 to W96
- Evolution of limb lean, limb fat, visceral adipose tissue (VAT) and subcutaneous adipose tissue (SAT), measured by DXA scan (Dual-energy X-Ray Absorptiometry), from D0 to W48 and W96 (DXA scan sub-study, 80 patients)

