12.3.2 Evaluation of the cardiovascular risk

For all included patients, the cardiovascular risk will be evaluated at Day 0, week 48 and week 96 using the Framingham equation adapted for France and the SCORE equation proposed by the European Society of Cardiology for countries with a low risk of cardiovascular event. The variables needed for the equations are: Age, sex, blood pressure, tobacco, total- and HDL-cholesterol, and diabetic defined by the fasting glycemia value or any anti-diabetic treatment. This evaluation supposes a standardization of the blood pressure measurements between the participating sites. The measurements have to be performed according to the "Recommendations for Blood Pressure Measurements in Humans and Experimented Animals" (Pickering et al. Circulation 2005).

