16.2.2 Statistical methods

The primary endpoint is the virological success up to week 48 defined by the absence of 2 consecutive HIV-RNA plasma VL > 50 copies/mL within 2 to 4 weeks.

The therapeutic success is defined by the absence of virological failure and the absence of treatment interruption due to adverse event judged by DSMB as related to the trial treatment or procedure up to week 96.

In particular:

- Patients with 2 or more consecutive missing HIV-1 RNA plasma viral load values or lost to follow up will be considered as patients with treatment failure (failing patients).
- Patients who discontinue the treatment due to adverse event judged by DSMB as related to the trial treatment or procedure will be considered as failing patients.
- Patients who discontinued the treatment due to adverse event judged by DSMB as NOT related to the trial treatment or procedure will not be considered as failing patients.
- Patients who gave up will not be considered as failing patients.
- Patients who discontinued the trial treatment for any reason other than a virological failure or adverse event judged by DSMB as related to the trial treatment will not be considered as failing patients.
- Patients with a missing HIV-1 RNA value between 2 documented HIV-1 RNA plasma viral loads \leq 50 copies/mL will not be considered as failing patients.

Analysis of the primary endpoint will be performed on both ITT and per protocol populations. The 95% two-sided confidence interval of the percentage of patients in therapeutic success will be calculated and raltegravir/etravirine will be considered as an acceptable strategy if the lower bound is greater than 90%.

The changes in continuous endpoints will be compared in the ITT population (LOCF or other imputation method to be defined in the statistical analysis plan) using a two-sided non-parametric paired Wilcoxon test with a 5 % type I error. We will use percentage and 95 % two-sided confidence interval to describe the qualitative endpoints, their change over time will be tested a McNemar test with a 5 % type I error.

The adverse events leading to a trial treatment discontinuation and the number of patients who discontinued the trial treatment, as well as the number and nature of grade 3 and 4 adverse events will be described.

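### Section 12.3.1 counts patients above the upper limit of normal for HDL-cholesterol as for the other four parameters, and no proportion with low HDL is planned (minor)

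*Combined protocol and SAP*

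**What the plan says.** Section 12.3.1 says that glucose and lipid metabolism "will be evaluated by measuring the fasting glycemia, triglycerides, total-cholesterol, LDL-cholesterol and HDL-cholesterol". The next sentence sets two summaries for these parameters at each visit where they are measured: "the median values and the proportion of patients above the upper normal will be reported and analyzed". HDL is named in the list, and neither sentence makes an exception for it.

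The related text elsewhere in the protocol is as follows.

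- Section 9.2 lists the evolution of the same five parameters as a secondary endpoint, without a cut-off.
- Section 16.2.2 tests changes in continuous endpoints "using a two-sided non-parametric paired Wilcoxon test with a 5 % type I error". For categorical endpoints it states "We will use percentage and 95 % two-sided confidence interval to describe the qualitative endpoints", and adds that "their change over time will be tested a McNemar test with a 5 % type I error".
- Section 12.3.2 feeds HDL into the Framingham and SCORE equations at D0, W48 and W96. The inputs are "Age, sex, blood pressure, tobacco, total- and HDL-cholesterol, and diabetic defined by the fasting glycemia value or any anti-diabetic treatment".
- Section 16.2.3 promises a detailed SAP before any analysis.

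**The concern.** A single upper-limit rule suits glycemia, triglycerides, total- and LDL-cholesterol, because a rising proportion is then bad news for each. HDL runs the other way. In a table with five such rows, four would read higher-is-worse and the HDL row would not, with nothing in the plan to warn the reader. The clinically relevant category, HDL below the lower limit, would be missing.

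Lipid evolution after leaving a boosted protease inhibitor is a named secondary endpoint, and limiting cardiovascular toxicity is part of the second trial hypothesis (section 5.6). HDL also responds to the choice of regimen: section 5.4.2 cites a trial in which HDL rose more on efavirenz than on etravirine (p=0.004). A categorical HDL summary that points the wrong way is therefore worth correcting, even though it is one line of one secondary analysis.

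**Working it through.** The point concerns direction, so most of the check sets sections side by side. The plan gives no figure to reproduce.

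**Step 1: is HDL inside the rule?** Yes. Section 12.3.1 names it among the five parameters, and the reporting sentence covers all of them.

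**Step 2: which direction does the protocol treat as favourable?** In support of raltegravir's metabolic profile, section 5.4.1 says: "There was a trend toward a greater decrease from baseline in the total cholesterol:HDL-cholesterol ratio for raltegravir". The same section cites a lower total-to-HDL ratio after a switch to raltegravir as an advantage. For a given total cholesterol, a higher HDL lowers that ratio. Section 9.2 also uses non-HDL-cholesterol and triglyceride/HDL-cholesterol; with the other lipids held fixed, higher HDL lowers both. The tail above the upper limit is thus the favourable one for HDL.

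**Step 3: is low HDL counted as a category anywhere?** No. The sections above define no lower-limit proportion. The lipid items of the grading scale in Appendix A6 are hypertriglyceridaemia and hypercholesterolaemia only.

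**Step 4: what would a McNemar test of this proportion do?** It compares the number of patients who cross the upper limit upwards with the number who cross it downwards. A patient whose HDL falls from the normal range to below the lower limit is not above the upper limit at either visit, so that patient contributes nothing.

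**Step 5: where would a fall in HDL still show?**

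- In the median, in the same sentence of section 12.3.1 and at the same visits.
- In the paired Wilcoxon test of section 16.2.2.
- In both risk equations, at D0, W48 and W96.
- In the triglyceride/HDL ratio, in the comparison of men and women up to W48 (section 9.2).

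The section 11.1 schedule also measures lipids at W12 and W24. At those two visits the risk equations are not run, and the upper-limit proportion is the only categorical HDL summary.

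**Step 6: illustration of size.** The documents give no HDL mean, SD, limits or expected change. Every input here is an assumption except the planned sample of 160: HDL normally distributed, mean 1.3 mmol/L, SD 0.3 or 0.4, a fall of 0.1, lower limit 1.0, upper limit 1.6 or 2.0. With Φ the standard normal distribution function, the proportion below the lower limit L is Φ((L − mean)/SD), and the proportion above the upper limit U is 1 − Φ((U − mean)/SD).

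| Summary | SD 0.3: before → after | SD 0.4: before → after |
|---|---|---|
| Below 1.0 | Φ(−1.00) = 15.9 % → Φ(−0.67) = 25.2 % | Φ(−0.75) = 22.7 % → Φ(−0.50) = 30.9 % |
| Above 1.6 | 1 − Φ(1.00) = 15.9 % → 1 − Φ(1.33) = 9.1 % | 1 − Φ(0.75) = 22.7 % → 1 − Φ(1.00) = 15.9 % |
| Above 2.0 | 1 − Φ(2.33) = 1.0 % → 1 − Φ(2.67) = 0.4 % | 1 − Φ(1.75) = 4.0 % → 1 − Φ(2.00) = 2.3 % |

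Low HDL rises by 9.3 or 8.2 percentage points, which is 160 × 0.093 ≈ 15 or 160 × 0.082 ≈ 13 patients. The proportion that the plan reports falls by 6.8 points with an upper limit of 1.6, and by 0.6 or 1.7 points with 2.0. The illustration shows how the two summaries can diverge. It does not predict what this trial would find.

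**The case against.** A reader might infer that the plan scores high HDL as an abnormality, that the McNemar test examines HDL with its sign reversed, or that a fall in HDL would pass as an improvement. The documents support none of these.

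- **No score.** Section 12.3.1 contains no score and no abnormality label. It reports a proportion, and counts only HDL values above the upper limit, not every rise.
- **No sign to reverse.** Section 16.2.2 states no direction of benefit. The usual two-sided McNemar test depends on the discordant pairs, and swapping the category labels leaves its p-value unchanged. Applying it to this proportion is itself an inference, since the endpoint in section 9.2 has no cut-off.
- **A fall would be seen.** The median stands in the same sentence, and the other analyses in step 5 use HDL in its true direction.
- **No fall is predicted.** Section 5.4.1 reports no significant HDL change in treatment-naïve patients starting raltegravir.
- **The detail may be settled elsewhere.** Section 12.3.1 sits in the chapter on biological samples and may be a drafting shortcut. The promised SAP is the natural place for the direction and source of each limit.

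All of this stands, and it keeps the point small. It does not remove the point: the sentence as written covers HDL, and the documents supply no low-HDL proportion. A SAP that carried the sentence over unchanged would inherit the problem.

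**Conclusion.** The concern holds as a minor one. The only categorical summary specified for HDL counts the favourable tail, and the unfavourable tail is not counted. That summary, and any McNemar test of it, does not measure adverse HDL change and could be misread in a table with the other four parameters. Low HDL values still enter the continuous analyses and the risk equations, so it would go too far to say that the plan ignores them.

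The effect is confined to one categorical summary of one component of a secondary endpoint. The primary endpoint, the sample size and the decision rule are unaffected. No size can be derived from the documents. The figures in step 6 rest wholly on assumed HDL values, and the change in the reported proportion depends strongly on the assumed upper limit.

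**What to change.** In section 12.3.1 and the SAP, keep the proportion above the upper limit of normal for fasting glycemia, triglycerides, total- and LDL-cholesterol. For HDL-cholesterol, report and test the proportion below the laboratory's lower limit of normal, sex-specific where the laboratory gives one. Name the source of the limits for all five parameters.

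The cost is one sentence in each document. No new measurement is needed: HDL is already collected, and section 18.8 already requires sites to hold laboratory normal ranges. Because Appendix A8 refers to first trial results, the amended text should be dated so that readers can see whether the low-HDL proportion was set before or after those results.

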12.3.2 Evaluation of the cardiovascular risk

For all included patients, the cardiovascular risk will be evaluated at Day 0, week 48 and week 96 using the Framingham equation adapted for France and the SCORE equation proposed by the European Society of Cardiology for countries with a low risk of cardiovascular event. The variables needed for the equations are: Age, sex, blood pressure, tobacco, total- and HDL-cholesterol, and diabetic defined by the fasting glycemia value or any anti-diabetic treatment. This evaluation supposes a standardization of the blood pressure measurements between the participating sites. The measurements have to be performed according to the "Recommendations for Blood Pressure Measurements in Humans and Experimented Animals" (Pickering et al. Circulation 2005).

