	
 - Modification of peripheral and central body fat distribution at W48 and W96 compared to D0 measured by DXA scan (Dual-energy X-Ray Absorptiometry) (DXA scan sub-study, 80 patients). - Evolution of bone mineral density measured by DXA scans at W48 and W96 compared to D0 (DXA scan sub-study, 80 patients). - To assess HIV-RNA viral load and Cmin (Minimal Drug Concentration) of raltegravir and etravirine at W48 in human male genital compartment (semen sub-study, 20 patients). - Evolution of the inflammation markers (IL-6hs, sCD14, sCD163, D-Dimers, IP-10, IgG, CRPus and insulin on frozen plasma aliquots from D0 to W48, and W96). - Evaluation of health-related quality of life with a self-assessment questionnaire at D0, W48, W96 and of the compliance with a self-assessment questionnaire at W-6/W-4, W48, W96. - 
 • Evaluation of the evolution of the cardio-vascular disease-related markers in women according to their ovarian reserve and their menopausal status - Evolution of the ovarian reserve from D0 to W48 measured by AMH on frozen aliquots - Evolution of the level of MCP1/CCL2 from D0 to W48 on frozen samples - Evaluation of the metabolic/inflammatory profile according to sex at inclusion and its evolution up to week 48 - Evaluation of metabolic profile, inflammatory, innate immune activation markers in women according to their status regarding ovarian reserve and menopausal status at inclusion and its evolution up to week 48
Methodology	Multicenter non-comparative phase II trial evaluating the capacity of the dual combination raltegravir/etravirine to maintain virological success defined as the absence of 2 consecutive plasma viral loads (VL) > 50 copies/mL within 2 to 4 weeks in virologically suppressed HIV-1 infected patients, of at least 45 years of age, switching from a boosted PI-containing regimen.
Estimated enrolment	By including 160 individuals and considering the strategy to be acceptable if at least 152 individuals maintain virological success, we will have a 95 % probability to discard a combination for which efficacy is smaller than 90 % and we will select with a power of 80 % a strategy for which the efficacy is above or equal to 95 %.

Study endpoints **Primary endpoint** Proportion of patients remaining, at week 48 on virological success defined as the absence of 2 consecutive HIV-RNA plasma VL > 50 copies/mL within 2 to 4 weeks interval.

Secondary endpoints

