The recent years have highlighted the cumulative toxicities of long-term exposure to antiretroviral drugs.

Cardiovascular disease is one of the most common comorbidities in the aging HIV-infected population [4-5]. Coronary artery disease (CAD) results from a combination of increasing age, traditional risk factor such as smoking, toxicity from long-term ART [6], and potentially related to HIV immune activation.

The French Hospital Database on HIV (ANRS CO4 FHDH) included over 80 000 patients followed over several years and measured the incidence of non-HIV related events. As early as 2003, ANRS CO4 FHDH showed that the risk of myocardial infarction (MI) was higher in HIV-infected patients exposed to PI than in the general population and dependent of cumulative exposure [7]. More recently ANRS CO4 FHDH showed that cumulative exposure to PI was associated with an increased risk of MI, and that the link to abacavir could not be considered causal [8]. We also showed a higher risk of MI in HIV infected patients than in the general population and the influence of both HIV replication and immunological status (CD4 nadir, current CD8 count) on the risk of MI, independently of traditional risk factors and exposure to antiretroviral drugs [9]. Exposure to PI was associated with a higher risk of MI [relative hazard (RH), 2.56; 95% confidence interval (CI), 1.03–6.34]. The expected incidence in the French general male population was 10.8/10 000 PY (Person-Year). The standardized morbidity ratios relative to the French general male population was 0.8 (95% CI, 0.5–1.3) for men exposed to PI for < 18 months, 1.5 (95% CI, 0.8–2.5) for men exposed for 18–29 months and 2.9 (95% CI, 1.5–5.0) for men exposed for > 30 months [8, 10].

Most of boosted PIs and the NNRTI efavirenz are associated to an increase in triglycerides and total cholesterol plasma levels [11]. In the ANRS CO8 APROCO COPILOTE cohort about 30% of patients developed hypertriglyceridemia. Prevalence of lipodystrophy and metabolic alterations and these alterations appear as early as 12 months after the initiation of PI therapy [12].

5.2.2 **Bone toxicity**

The prevalence of osteopenia and osteoporosis in HIV-infected individuals is higher in HIV-infected compared with HIV-negative individuals ranging, from 23 to 65% for osteopenia and from 3 to 22% for osteoporosis according to the studies [13-16] with, as consequence, a higher prevalence of patients with fracture ($p < 0.0001$) [17].

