7 EXPERIMENTAL DESIGN

7.1 Main study

ANRS 163 ETRAL is a multicentre non-comparative phase II trial evaluating, in fully suppressed HIV-1-infected patients, of at least 45 years of age, with a suppressed viremia, the capacity of a dual raltegravir/etravirine antiretroviral regimen to maintain the virological success defined as two consecutive HIV-RNA plasma viral loads > 50 copies/mL within 2 to 4 weeks. Eligible patients must be under a stable PI-containing ARV regimen for at least 6 months and they must be fully suppressed within the 24 months prior the screening visit (W-6/W-4), as confirmed by 4 documented viral loads (e.g. 2 measurements per year during the past 24 months and not more than 1 HIV-RNA plasma viral load between 51 and 200 copies/mL).

All PI-containing baseline ARV regimens are eligible except those containing raltegravir and/or etravirine.

At Day 0, patients eligible according all criteria detailed in paragraph 8 will be switched to the dual raltegravir (400 mg BID) plus etravirine (200 mg BID) regimen.

Any SAE considered by the investigator and/or the sponsor as potentially related to the trial treatments will be reviewed and evaluated by DSMB.

For all patients, during the 96 first weeks of the trial, a summary of the virological data including HIV-RNA viral loads and virus strains genotypes will be regularly submitted to the DSMB for review.

The immunologic analysis of the evolution of the inflammation markers will be performed on frozen plasma aliquots from whole blood samples collected at specific time points: D0, W48, and W96. The markers of interest are: IL-6hs, sCD14, sCD163, D-Dimers, IP-10, IgG, CRPus and insulin.

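### Framingham and SCORE take age as an input and their change is tested against zero in a single arm, so ageing during follow-up enters the result unless age is held at its D0 value

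*Combined protocol and SAP*

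**What the plan says.** Section 12.3.2 provides that for all included patients "the cardiovascular risk will be evaluated at Day 0, week 48 and week 96", using a Framingham equation adapted for France and the SCORE equation for low-risk countries. On the inputs it says "The variables needed for the equations are: Age, sex, blood pressure, tobacco, total- and HDL-cholesterol", to which it adds diabetes.

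Section 9.2 lists as a secondary endpoint "Evolution of the calibrated Framingham risk score and of the SCORE risk equation including HDL cholesterol", from D0 to W48 and W96.

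Section 16.2.2 gives the analysis in general terms: "The changes in continuous endpoints will be compared in the ITT population", by a "two-sided non-parametric paired Wilcoxon test with a 5 % type I error". It does not name the risk scores, but they are continuous endpoints defined by their change.

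On design, section 7.1 states "ANRS 163 ETRAL is a multicentre non-comparative phase II trial". No section says whether the age entered at W48 and W96 is the attained age or the age at D0.

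**The concern.** The paired test takes zero change as its null hypothesis. For an endpoint such as LDL-cholesterol, zero is a reasonable stand-in for no effect of the switch. For a score that contains age it is not. A patient whose blood pressure, lipids, smoking and diabetes status are exactly as at D0 still scores higher later, because that patient is older. The protocol itself treats age as a driver of risk in section 5.2.1: "Coronary artery disease (CAD) results from a combination of increasing age, traditional risk factor such as smoking". The shift has the same sign in every patient and is unrelated to the regimen, and there is no control group in which to observe and subtract it.

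What is at stake is the reading of the trial's second hypothesis (5.6), that the switch limits long-term toxicity, cardiovascular toxicity included. A true gain from modifiable factors can be partly or wholly cancelled in the score, or an unchanged profile can come out as a significant rise. The problem is larger at W96, where the ageing interval is twice as long.

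**Working it through.** **Inputs from the documents.** Score times D0, W48 and W96 (12.3.2); age as an input (12.3.2); paired Wilcoxon, two-sided 5% (16.2.2); single arm (7.1); planned n = 160 (synopsis, estimated enrolment: "By including 160 individuals and considering the strategy to be acceptable"). The plan states no effect size, SD or power for the risk scores, so there is no figure of its own to reproduce.

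**Assumptions, not in the documents.** Relative rise in score per year of age, other factors constant: g = 3% to 10%. SD of the within-patient change in log score: 0.2 to 0.4. Log changes are taken as normal.

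**Step 1: ageing interval.** 48 × 7 / 365.25 = 0.92 years; 96 × 7 / 365.25 = 1.84 years.

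**Step 2: drift with everything but age unchanged**, (1 + g)^t − 1:

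| g per year | W48 | W96 |
|---|---|---|
| 3% | +2.8% | +5.6% |
| 5% | +4.6% | +9.4% |
| 7% | +6.4% | +13.3% |
| 10% | +9.2% | +19.2% |

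A 10.0% risk would therefore read 10.3% to 10.9% at W48 and 10.6% to 11.9% at W96.

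**Step 3: effect on the planned test when the switch does nothing.** The paired Wilcoxon test was simulated with n = 160 and 4,000 trials per setting. The entries are the probability of a significant rise; the nominal value is 2.5%.

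| g per year | W48, SD 0.2 / 0.3 / 0.4 | W96, SD 0.2 / 0.3 / 0.4 |
|---|---|---|
| 0 (age fixed) | 2.8% / 2.6% / 2.2% | 2.2% / 2.4% / 2.9% |
| 3% | 37% / 21% / 13% | 92% / 62% / 38% |
| 5% | 79% / 45% / 28% | 100% / 96% / 78% |
| 10% | 100% / 94% / 77% | 100% / 100% / 100% |

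Hand check of one cell (5%, SD 0.3, W48): the mean log shift is ln(1.05) × 0.92 = 0.0449, the standard error is 0.3/√160 = 0.0237, and the ratio is 1.89. The normal approximation gives P(Z > 1.96 − 1.89) = P(Z > 0.07), about 47%, against 45% simulated.

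**Step 4: effect when there is a true benefit.** Take a 10% relative fall from modifiable factors and g = 5%. The net score ratio is 0.90 × 1.046 = 0.941 at W48 and 0.90 × 1.094 = 0.985 at W96, so the visible fall is 5.9% and then 1.5%. Simulated power to show a fall with age updated is 96% / 70% / 47% at W48 and 16% / 10% / 7% at W96 (SD 0.2 / 0.3 / 0.4). With age fixed at D0 it is between 89% and 100% at both times.

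**The case against.** Several points on the other side carry weight.

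- *The text does not say that attained age is used.* Correct. Section 12.3.2 only lists age as an input, 16.2.2 covers the scores only through a general phrase, and 16.2.3 promises a detailed SAP. Still, re-evaluating risk at each visit most naturally means current inputs. For continuous endpoints, 16.2.2 expressly defers only the imputation method. A fixed-age rule has to be written somewhere, and it is not in these documents.
- *Other influences may push the score the other way.* This stands. Section 11.11.3 provides for lipid-lowering treatment during follow-up, which would lower the score. Smoking changes and regression to the mean are also uncontrolled in a single arm. A reader might infer that the test as a whole is biased against the switch; the documents do not support that. Only the ageing component has a known sign. Equally, fixing age removes one distortion and does not isolate the regimen's effect.
- *A false worsening is not certain.* A reader might infer that an unchanged profile will be reported as significantly worse. At 3%/year that would usually not happen at W48 (13% to 37%).
- *The size is assumed.* Also true, and the SD matters a great deal. This is why ranges are shown.
- *Attained-age risk is a legitimate quantity.* It describes a patient's current absolute risk. The criticism is of testing its change against zero and attributing the result to the regimen.
- *The consequence is limited.* The scores are one of many secondary endpoints, and the lipids are separate endpoints (9.2) summarised by visit (12.3.1), so a lipid benefit would remain visible there.

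**Conclusion.** The point stands as an analysis choice to correct in a secondary endpoint. Age is an input, the change from D0 falls under a test against zero, there is no control arm, and nothing fixes age. On the natural reading, zero change is therefore the wrong null for no effect of the switch. Ageing adds an upward drift that can mask a benefit or make an unchanged profile appear to worsen; the sign of the net bias is not established.

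The direction of the ageing component is secure. Its size rests entirely on the assumed age slope and SD, and so do the error rates above. The problem is worse at W96 than at W48 throughout the assumed range. The primary virological conclusion is not affected.

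**What to change.** In section 12.3.2 and in the SAP, state that the W48 and W96 Framingham and SCORE values used for the paired test are calculated with age held at its D0 value, with all other inputs as measured at the visit. Report attained-age scores descriptively beside them, without attributing their change to the regimen. Say in the report that the fixed-age change may still reflect lipid-lowering treatment, smoking changes and regression to the mean.

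The cost is one line of programming. Birth date is collected at screening (11.3), and no new data, visit or patient is needed. Appendix A8 shows that first results already exist. If the risk scores have been analysed, the fixed-age result can be added and labelled as an addition.
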